4.1.2. Analysis Methods

Intent-to-treat population will be used for efficacy endpoints. Analysis for efficacy endpoints will be repeated on the efficacy analysis set.

The ASAS20 and ACR20 response evaluations will be performed on week 0, week 4, week 14 and week 24. The scores obtained from the respective domains will decide the responder for

ASAS20 or ACR20 criteria. Proportion of patients who achieve ASAS20 or ACR20 criteria at week 24 will be calculated, along with a 95% confidence interval.

For ASAS20, if data for percent improvement from baseline is missing at a particular assessment visit, then the response for the subject at that visit will be considered as missing.

If a subject's baseline value is zero (i.e. for ACR no disease activity for one assessment,) or missing, the subject should be considered as non-responder.

If all its components for a composite endpoint (i.e. score for subdomain as captured in CRF) are missing, the response for the endpoint at the particular visit will be set as missing; if not all its components are missing, LOCF will be used to impute the missing components and the value of the composite endpoint will be derived based on the imputed components.

If subject discontinues due to lack of efficacy, subject should be considered as non-responder.

If there is an Increase in the dose of MTX subject should be considered as non-responder.

The analysis will be done separately for each indication.

The scores for individual domains for both the ASAS20 and ACR20 will be descriptively summarized at all analysis visits.

The individual domain scores will be listed for each criteria.

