#### **9.1.2. Screening Visit: Visit 1 / Day (-7 to -1)**

After informed consent has been obtained at screening, each patient will be assigned a unique number for the duration of the trial.

Indian patients who are eligible to receive SIMPONI® will be considered in the present study. Prior to data collection, all patients and/or their legally acceptable representative (LAR) where applicable will sign an informed consent form (ICF) allowing data collection and source data verification in accordance with local regulations.

The below mentioned procedure and measurements will be performed at screening visit:

- Obtaining written informed consent
- Confirming eligibility criteria check
- Collection of demographic data
- Measurement of height and weight
- Physical examination
- Examination of vital signs (blood pressure, heart rate, respiratory rate and temperature)
- Confirmation of diagnosis of AS or PsA and history of the disease
- Other medical history
- Electrocardiogram
- Serum Pregnancy test
- HIV (ELISA test), HBV (HBsAg test), and HCV (Anti-HCV test)
- Routine laboratory tests: haemoglobin, haematocrit, platelet count, total and differential WBC count, blood urea nitrogen (BUN), creatinine, total bilirubin, alkaline phosphatase, ALT, AST, sodium, potassium, blood glucose, albumin and total protein
- Qualitative urinalysis (dipstick) of protein, glucose, ketones, blood, leucocyte esterase or nitrate. If dipstick urine analysis is positive for blood, WBC (eg, leucocyte esterase or nitrates), or protein, then complete urinalysis (dipstick and microscopy) will be performed.
- Chest x-ray
- QuantiFeron-TB Gold test and tuberculin skin test

- Documentation of HLA B-27 status
- Erythrocyte sedimentation rate (ESR)
- CRP
- Bath AS Disease Activity Index (BASDAI) evaluation,
- Spinal Pain (Numerical Rating Scale [NRS]) assessment
- Concomitant medications review
- AE/SAE review (the collection of AE information will start from the time of provision of written informed consent)

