### **9.1.3. Treatment and Assessment Visits**

#### **Week 0 (Visit 2/Day 1)**

Patients who qualify will be enrolled in the study and will receive the study drug on confirmation of their enrolment status. Before the first administrations of the study drug (Week 0, Day 1), assessments/procedures should be performed as indicated in TIME AND EVENTS SCHEDULE. Patients must meet all of the inclusion and none of the exclusion criteria that are assessable in the clinic at the time of the baseline visit before enrolment in the study.

The below mentioned procedure and measurements will be performed at this visit:

- Eligibility Criteria
- AE/SAE review
- Concomitant medications review
- Vital signs (blood pressure, heart rate, respiratory rate and temperature)
- Urine pregnancy test
- TB suspicion & evaluation (If TB is suspected at any time during the study, a chest x-ray, QuantiFERON-TB Gold test, and tuberculin skin test should be performed)
- ASAS20 (for AS patient) response evaluation:
  - BASDAI evaluation
  - Bath AS Functional Index (BASFI) evaluation
  - Spinal Pain (NRS) assessment
  - Patient global assessment (PGA) (NRS)
- ACR20 (for PsA patient) response evaluation:
  - tender and swollen joint count assessment,
  - Patient's assessment of pain,
  - Patient's global assessment of disease activity,
  - Physician's global assessment of disease activity,
  - Health Assessment Questionnaire (HAQ)
  - ESR
  - CRP
- Study drug administration
- Study drug injection-site evaluation

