2.4. Baseline

Baseline is defined as the last observation prior to the start of the first study drug administration.

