2.6. Handling Missing Data

For subjects who discontinue treatment but continue to be followed up and for whom some endpoint component data are missing, the last observation carried forward will be followed to Week 14 or Week 24 as applicable.

For a composite endpoint, if all its components are missing, no imputation will be done; if not all its components are missing, LOCF will be used to impute the missing components.

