weighting, the mean of the two scores relating to morning stiffness is taken. The resulting 0 to 50 score is divided by 5 to give a final 0 to 10 BASDAI score. A BASDAI score of 4 or greater is considered to be indicative of active AS disease.

The ACR response criteria (ACR20) is defined as

- **$\geq 20\%$ improvement in swollen joint count** – ACR swollen joint count, an assessment of 28 or more joints, which includes the shoulders, elbows, wrists, metacarpophalangeal (MCP) 1-5, proximal interphalangeal (PIP) 1-5 and the knees, bilaterally. Joints are classified as either *swollen* or *not swollen*.
- **$\geq 20\%$ improvement in tender joint count** – ACR tender joint count, an assessment of 28 or more joints, which includes the shoulders, elbows, wrists, MCPs 1-5, PIPs 1-5 and the knees, bilaterally. The joint count should be done by scoring several different aspects of tenderness, as assessed by pressure and joint manipulation on physical examination. The information on various types of tenderness should then be collapsed into a single *tender*-versus-*nontender* dichotomy.
- **$\geq 20\%$ improvement in 3 of the following 5 assessments:**
 - a) **Patient's assessment of pain** - A horizontal visual analogue scale (VAS) (usually 10 cm) assessment of the patient's current level of pain. The patient will be asked for severity of pain and he/she should be marked on the scale as per severity. The left side of VAS is of 'No Pain' and right side is of 'Most Severe Pain'.
 - b) **Patient's global assessment of disease activity** – A simple patient-reported VAS which assesses the patient's general health and the effect of their arthritis at that point in time. The VAS is scored by measuring from 0 to where the patient marks on the line.
 - c) **Physician's global assessment of disease activity** - A physician's global assessments of disease activity will be recorded on a VAS Scale.
 - d) **Patient's assessment of physical function as measured by the Health Assessment Questionnaire** - The functional status of the patient will be assessed by means of the Disability Index of the HAQ. This 20- question instrument assesses the degree of difficulty a person has in accomplishing tasks in 8 functional areas (*dressing, arising, eating, walking, hygiene, reaching, gripping, and activities of daily living*). Responses in each functional area are scored from 0, indicating '*no difficulty*', to 3, indicating '*inability to perform a task in that area*'.

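### SAP 4.1.2 makes a PsA patient an ACR20 non-responder for one zero baseline assessment, although the SAP's own ACR20 needs only 3 of the 5 non-joint assessments to improve

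*SAP*

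**What the plan says.** SAP 4.1.1 defines ACR20 as at least 20% improvement in the swollen joint count, the same in the tender joint count, and at least 20% "improvement in 3 of the following 5 assessments": patient pain, patient global, physician global, HAQ and acute-phase reactant. Protocol 9.4 and Appendix G have the same structure, and neither contains a rule for a zero baseline.

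SAP 4.1.2 adds one, for any patient whose "baseline value is zero (i.e. for ACR no disease activity for one assessment,) or missing, the subject should be considered as non-responder".

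In the next paragraph 4.1.2 has a sentence on missing components, under which the response is worked out after filling the gaps. SAP 2.6 has the same provision: "if not all its components are missing, LOCF will be used to impute the missing components". On the baseline value itself, SAP 2.4 states: "Baseline is defined as the last observation prior to the start of the first study drug administration".

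**The concern.** The trigger in 4.1.2 is a single assessment, but the consequence falls on the whole patient. The definition in 4.1.1 tolerates two non-improving assessments out of five. The two rules therefore disagree for any patient with one or two zeros among the five at baseline who improves on both joint counts and on at least three of the rest.

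The missing-baseline half of the sentence is open as well. It may mean one item or the entire baseline, and the SAP does not say whether it or the LOCF sentence takes precedence. Two programmers could derive different responder flags for the same patient.

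At stake is the accuracy of the ACR20 proportion and of its confidence interval, which 4.1.2 plans explicitly for Week 24. Taken alone, the rule can only lower the rate.

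**Working it through.** The plan gives no figure to reproduce. The 50 PsA patients are a regulatory requirement, and there is no test, power calculation or assumed response rate. The check compares the two rules and then sizes the difference.

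**1. Can the conflicting case occur?** On the HAQ, SAP 4.1.1 states "Responses in each functional area are scored from 0, indicating" no difficulty, so a total of zero is an allowed score. Protocol 4.1 admits PsA patients with any swollen or any tender joint and sets no HAQ minimum. A physician global of zero is unlikely, because the same section requires active PsA as judged by the treating physician.

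**2. Counter-example.** Baseline HAQ is 0; both joint counts and the other four assessments each improve by 50%.
- Definition (4.1.1): both joint counts met, 4 of 5 met, so responder.
- Baseline rule (4.1.2): one assessment zero at baseline, so non-responder.

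**3. All patterns, given that both joint counts improve.** A zero-baseline assessment is treated as not improved. The table counts the improved/not-improved patterns of the remaining assessments. These are counts, not probabilities.

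| Zeros among the five | Patterns of the rest | Meet the definition | Responders under 4.1.2 read literally |
|---|---|---|---|
| 1 | 2^4 = 16 | 4 + 1 = 5 | 0 |
| 2 | 2^3 = 8 | 1 | 0 |
| 3 | 2^2 = 4 | 0 | 0 |

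The rules conflict with one or two zeros and agree from three upwards.

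**4. Zero joint count.** A 20% improvement in a mandatory component cannot be shown, so non-response is compatible with the definition and there is no conflict.

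**5. Missing baseline.** In the Time and Events Schedule, pain, both globals, HAQ and the joint counts are first due at Week 0, so a missed baseline has no earlier value to carry forward. ESR and CRP are also taken at screening, and under SAP 2.4 that value would serve as baseline. A patient missing only the baseline HAQ is a non-responder if one missing item triggers the rule. If the rule means a wholly missing baseline, the SAP does not settle the outcome.

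**6. Size.** Let n be the number analysed and r the affected patients who meet the definition. Loss in percentage points = 100 × r / n.
- Per reclassified responder: 100/50 = 2.0; 100/45 = 2.2; 100/40 = 2.5 (45 and 40 are assumed).
- With k affected patients at n = 50 (k is assumed), r lies between 0 and k whatever the correlation between assessments:

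| k | Bounds | r = 0.6k (assumed) | r = 0.4k to 0.8k (assumed) |
|---|---|---|---|
| 1 | 0–2.0 | 1.2 | 0.8–1.6 |
| 3 | 0–6.0 | 3.6 | 2.4–4.8 |
| 5 | 0–10.0 | 6.0 | 4.0–8.0 |

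For scale, 30/50 = 60.0% (exact 95% CI 45.2–73.6%) becomes 27/50 = 54.0% (39.3–68.2%) if three true responders are reclassified. The exact (Clopper-Pearson) interval is my choice; the SAP names no method.

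**The case against.** **The authors may have meant the component, not the patient.** Possibly, but the text names the subject, as do the neighbouring rules on lack of efficacy and methotrexate increase, which are plainly patient-level. If the component was meant, the sentence needs correcting; if the patient was meant, it contradicts 4.1.1.

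**LOCF is meant for post-baseline visits.** The first paragraph of SAP 2.6 points that way: it concerns patients who stop treatment and carries values to Week 14 or 24. The second paragraph of 2.6 and the LOCF sentence in 4.1.2 state no such limit. Since LOCF can supply almost nothing at baseline, the practical clash is narrow. What stays open is whether one missing item is enough.

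**The rule does useful work for joint counts.** This stands. Percent change from zero is undefined, and the sentence settles that case as non-response. That part should be kept.

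**Affected patients may be rare.** This also stands. A HAQ of zero means no difficulty in all eight areas in a patient with active disease, and the patient must also have both joint counts above zero and improving. The loosest part of the entry criterion mainly admits patients with one joint count at zero, for whom the rules agree. Nothing in the documents suggests the harmful case is common.

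**The consequences are limited.** There is no hypothesis test, safety is the primary objective, the bias cannot overstate efficacy, and the listed domain scores would allow re-derivation. This limits the severity but does not remove the contradiction.

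**Conclusion.** The concern holds. As written, SAP 4.1.2 reports as failures some patients who satisfy the ACR20 definition in SAP 4.1.1, and no other passage cures this. Confidence is high for the conflict in wording. The total effect cannot be derived: only the 2.0 points per reclassified responder at n = 50 is firm, and the numbers affected and their response rates are assumptions. The drop from 60.0% to 54.0% is the upper bound for three affected patients, not an expected value. Because ACR20 is a secondary, descriptive endpoint, this should be fixed before the responder derivation is run, but no trial decision turns on it.

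**What to change.** Replace the sentence in SAP 4.1.2 with three rules:

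1. A zero or missing baseline in one of the five non-joint ACR assessments counts as not improved for that assessment only; improvement in 3 of the 5 is still required.
2. A zero or missing baseline tender or swollen joint count makes the patient an ACR20 non-responder.
3. These baseline rules take precedence over LOCF, which applies to post-baseline components only.

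While the section is open, add a line saying whether any baseline rule applies to ASAS20; that is a clarification, separate from the contradiction above.

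The cost is about four sentences in 4.1.2, a matching line in 2.6 and one change to the responder derivation. No new data or visits are needed, because the baseline components are already collected, summarised and listed.

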2.2. Analysis Sets

The analysis sets used in this study are Safety and Intent to Treat (ITT) analysis sets. The efficacy endpoints will be assessed by using ITT analysis set and Efficacy Analysis Set, and safety endpoints by Safety Analysis set.

Safety Analysis Set: The Safety Analysis set includes all subjects who were enrolled and received at least one dose of the study drug.

Intent to Treat (ITT) Analysis Set: The ITT population will include all subjects who were enrolled and received at least one dose of the study drug and have completed Week 24 visit

Efficacy Analysis Set for AS subjects: Efficacy analysis set for AS subjects includes all AS subjects who were enrolled and received at least one dose of the study drug and having at least one non-missing post-baseline ASAS20 score for AS indication.

Efficacy Analysis Set for PsA subjects: Efficacy analysis set for PsA subjects includes all PsA subjects who were enrolled and received at least one dose of the study drug and having at least one non-missing post-baseline ACR20 score for PsA indication.

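### At Week 24 the repeat analysis on the Efficacy Analysis Set is only weakly sensitive to drop-out for reasons other than lack of efficacy, so it largely repeats the completer-only ITT result

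*SAP*

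**What the plan says.** Two sets carry the efficacy analysis. SAP 2.2 restricts the ITT set to patients who "received at least one dose of the study drug and have completed Week 24 visit", and Protocol 11.1.2 agrees. (The protocol synopsis defines ITT by dosing alone.) The Efficacy Analysis Set for AS drops the Week 24 condition and asks instead for dosed patients "having at least one non-missing post-baseline ASAS20 score for AS indication". The PsA set has the same form with ACR20. SAP 4.1.2 makes ITT the main set and adds: "Analysis for efficacy endpoints will be repeated on the efficacy analysis set".

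On absent data, SAP 2.6 states: "For a composite endpoint, if all its components are missing, no imputation will be done". SAP 4.1.2 repeats the rule for response status: if all components are absent, "the response for the endpoint at the particular visit will be set as missing". Last observation carried forward fills only a composite that is partly missing.

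Non-response is a separate status in SAP 4.1.2. It applies to a zero or missing baseline value and in two further cases: "If subject discontinues due to lack of efficacy, subject should be considered as non-responder", and "If there is an Increase in the dose of MTX subject should be considered as non-responder".

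**The concern.** A second analysis on a wider set would normally show how far the completer result depends on who stayed. Here the wider set admits patients who left early, but the missing-response rule then appears to remove most of them from the Week 24 proportion.

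SAP 3.2 lists 15 reasons for discontinuation. Only one of them, lack of efficacy, leads to non-response. A patient who leaves because of an adverse event, death, loss to follow-up, withdrawal, non-compliance, disease relapse or progressive disease, with nothing recorded in the Week 24 window, has a missing response unless another non-responder rule applies.

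The endpoint is the proportion of AS or PsA patients who respond. If both Week 24 figures describe mainly those who stayed, close agreement between them could be read as evidence that drop-out did not matter. It would not be such evidence.

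**Working it through.** **Plan's own figure.** There is none to reproduce. The sample size (50 AS + 50 PsA = 100) is a regulatory number, and the documents give no drop-out or response rate.

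**Inputs from the documents.** N = 50 dosed per indication (SAP 1.4). Withdrawn patients are not replaced (Protocol 10.3). The Week 24 efficacy window is Days 134 to 203 (SAP 2.1, Table 2).

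**Assumptions.** Response among completers is about 70%. Drop-out is 10%, 20% or 30%. Every drop-out has an earlier post-baseline score but no data in the Week 24 window. No patient has a methotrexate increase.

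**Formulas.** Let c be the completers, x the responders among them, and e the drop-outs for lack of efficacy.

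- ITT: x / c
- Repeat analysis, missing responses left out: x / (c + e)
- All dosed, no data scored as non-response: x / N

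**Step 1: no drop-out for lack of efficacy (e = 0).** The first two formulas are then identical.

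| Drop-out | ITT and repeat analysis | All dosed | Gap (points) |
|---|---|---|---|
| 5 (10%) | 31/45 = 68.9% | 31/50 = 62.0% | 6.9 |
| 10 (20%) | 28/40 = 70.0% | 28/50 = 56.0% | 14.0 |
| 15 (30%) | 24/35 = 68.6% | 24/50 = 48.0% | 20.6 |

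The gap equals completer response times the drop-out fraction, for example 0.70 × 0.20 = 14.0 points. At 20% drop-out the exact 95% intervals are 53.5% to 83.4% (28/40) and 41.3% to 70.0% (28/50).

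**Step 2: some drop-out for lack of efficacy (20% drop-out).**

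- e = 2: 28/42 = 66.7%
- e = 5: 28/45 = 62.2%

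The repeat analysis moves 3.3 or 7.8 points from the ITT 70.0%, against 14.0 for all dosed.

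**Step 3: other readings (20% drop-out, e = 0).**

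- If missing responses stay in the denominator: 28/50 = 56.0%.
- If the last completed assessment is used, as Protocol 10.1 suggests: from 28/50 = 56.0% (none of the 10 last seen as a responder) to 38/50 = 76.0% (all of them).

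**Step 4: Week 14.** Suppose 5 of the 10 drop-outs left after a Week 14 assessment, the other 5 have no Week 14 data, and the 40 completers have 28 responders at Week 14. ITT gives 28/40 = 70.0%. The Efficacy Analysis Set gives 28/45 = 62.2% to 33/45 = 73.3%. The two sets do differ here.

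**The case against.** A reader might infer that the repeat analysis cannot show any effect of drop-out and must agree with ITT by construction. The documents do not support that, for four reasons.

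- **Lack of efficacy.** These drop-outs count as non-responders in the repeat analysis, and fall outside ITT if they did not complete Week 24. Step 2 shows the estimate moving.
- **Early assessments.** Protocol 10.2 says stopping treatment does not automatically mean leaving the study, and calls for the Week 24 evaluations at early discontinuation. Protocol 10.3 asks for the end-of-treatment assessments at withdrawal. An assessment on Days 134 to 203 can supply a Week 24 response.
- **Week 14.** The repeat analysis keeps patients who left between Weeks 14 and 24 with Week 14 data.
- **Denominator.** The SAP never says that a missing response leaves the proportion. If the set size is the denominator, the Step 1 examples already give the all-dosed figures.

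These points limit the concern but do not remove it. Under Table 2 an assessment before Day 134 falls in an earlier window. SAP 2.1 labels the visit at study discontinuation as End of Study, for which Table 2 has no row. On the denominator, SAP 4.1.2 treats missing and non-responder as different statuses. Keeping missing responses in the denominator would make them the same in the reported proportion, so leaving them out is the natural reading, though it remains an inference.

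Protocol 10.1 points another way: it takes the last completed assessment of patients who stop treatment early into the analysis. That conflicts with setting the response to missing. It also sits badly with the missing-data paragraph of Protocol 11, which allows carry-forward for partly missing components and plans no other imputation.

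**Conclusion.** The concern holds in limited form. At Week 24 the repeat analysis is only weakly sensitive to drop-out for reasons other than lack of efficacy, and no planned analysis clearly counts every dosed patient without Week 24 data as a non-responder. Both Week 24 figures therefore rest mainly on patients who stayed.

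Under the assumptions of Step 1 the gap to an all-dosed analysis is about 7 to 21 points at 10% to 30% drop-out. It shrinks if drop-out is low, or if leavers are assessed within the window. If some leave for lack of efficacy, the repeat analysis itself moves closer to the all-dosed figure.

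A reader might also take the gap as the amount by which true response is overstated. The documents do not support that: the non-responder result is a conservative sensitivity estimate, and under the Protocol 10.1 reading the figure could lie above the completer rate. The unstated denominator and the conflict with Protocol 10.1 matter in their own right, since one 20% drop-out example gives anything from 56.0% to 76.0%.

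Efficacy is a secondary, descriptive objective with no hypothesis test. This should be corrected, but it does not touch the primary safety objective.

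**What to change.** 1. In the repeat analysis, use all dosed patients of the indication as the denominator at Weeks 14 and 24. Score a patient with no efficacy data for that visit as a non-responder, for both ASAS20 and ACR20. This replaces the condition of at least one post-baseline score.
2. Show the observed-case proportion beside it, with the number missing and the reasons.
3. State the denominator of every reported proportion.
4. Reconcile SAP 4.1.2 with Protocol 10.1 on how the last assessment of an early discontinuer is used.

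The cost is SAP wording and an extra table row. The downside is a less favourable reported response rate, which should be labelled as a conservative sensitivity estimate and not as the true rate.
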